1.3.2.2.2 OVERVIEW OF EFFICACY

1.3.2.2.2.1 Ovarian Cancer Treatment Indication

On 19 December 2016, the FDA granted accelerated approval, followed by regular approval in April 2018, for the marketing of rucaparib (Rubraca[®]) for monotherapy treatment of patients with deleterious BRCA mutation (germline and/or somatic) associated EOC, FTC, or PPC who have been treated with ≥ 2 chemotherapies.¹⁴ In May 2018, the European Commission authorized rucaparib (Rubraca) as monotherapy treatment of adult patients with platinum-sensitive, relapsed or progressive, BRCA-mutated (germline and/or somatic), high-grade EOC, FTC, or PPC, who have been treated with 2 or more prior lines of platinum-based chemotherapy, and who are unable to tolerate further platinum-based chemotherapy.¹⁵ The recommended dose of rucaparib is 600 mg BID.

The basis for the approval of rucaparib as monotherapy for the treatment of ovarian cancer are the data sets and analyses for patients with advanced ovarian cancer comprising the primary efficacy analysis population. The primary efficacy analysis population included 106 patients, of whom 79 were platinum-sensitive, pooled from the open-label, single-arm Phase 2 studies, Study CO-338-010 Part 2A and Study CO-338-017 Parts 1 and 2, with BRCA-mutant ovarian cancer, who had received ≥ 2 prior chemotherapy regimens, at least 2 of which were platinum-based, and who had received at least 1 dose of 600 mg rucaparib.¹⁴

The primary endpoint on which approval was based is investigator-assessed ORR per Response Evaluation Criteria in Solid Tumors (RECIST) Version 1.1 (v1.1), with ORR by central independent radiology review (IRR) conducted as a supportive analysis. ORR by investigator was 53.8%, while ORR by IRR was 41.5%, confirming the results of investigator assessment for this endpoint.¹³ Responses were durable, indicated by a duration of response (DOR) by investigator assessment of approximately 9.2 months.¹³

1.3.2.2.2 Ovarian Cancer Maintenance Indication

In April 2018, rucaparib (Rubraca) was approved in the US by the FDA for maintenance treatment for adult patients with recurrent EOC, FTC, or PPC who are in a complete or partial response to platinum-based chemotherapy.¹⁴ Efficacy of rucaparib monotherapy for patients with advanced ovarian cancer in the maintenance setting was demonstrated from Study CO-338-014 results showing significant benefit of rucaparib compared to placebo across primary, secondary, and exploratory endpoints.¹⁶ In this study, investigator-assessed PFS was the primary efficacy endpoint, with PFS by blinded central IRR conducted as a key, stand-alone, secondary endpoint. Rucaparib maintenance treatment significantly improved PFS compared with placebo in all primary analysis groups of patients with recurrent ovarian cancer after a complete or partial response to platinum-based therapy (Table 1). Overall, rucaparib as maintenance treatment reduced the risk of progression by 63.5% (hazard ratio 0.365 [95% CI, 0.295 0.451]; $p < 0.0001$) in the ITT population, demonstrating a strong treatment effect over placebo. Analysis of non-nested, non-overlapping patient subpopulations indicate that the significant improvement in PFS observed in the ITT population was not driven only by the HRD or tBRCA (tumor tissue mutation in BRCA) subpopulations (Table 1). Nearly half (44.6%) of the patients in the rucaparib group showed benefit at 1 year compared to 8.8% in the placebo group.¹⁶ At 18 and 24 months, 32.0% and 26.0%, respectively, of patients who received rucaparib were still progression-free compared to 5.8% and 2.6% in the placebo group.¹⁶ These investigator-assessed results were confirmed by results of central IRR assessment (Table 1).¹⁶

Table 1. Progression-free Survival per Investigator and per IRR in Primary Analysis Populations in Study CO-338-014

Analysis Population	PFS by Investigator Review (Primary Endpoint)		PFS by Blinded, Central IRR (Key Secondary Endpoint)	
	Median PFS (months) Rucaparib vs Placebo ^a	Hazard Ratio ^b	Median PFS (months) Rucaparib vs Placebo ^a	Hazard Ratio ^b
Primary Analysis Groups				
tBRCA (rucaparib n = 130; placebo n = 66)	16.6 vs. 5.4 (p < 0.0001)	0.231 (p < 0.0001)	26.8 vs. 5.4 (p < 0.0001)	0.201 (p < 0.0001)
HRD (rucaparib n = 236; placebo n = 118)	13.6 vs. 5.4 (p < 0.0001)	0.317 (p < 0.0001)	22.9 vs. 5.5 (p < 0.0001)	0.336 (p < 0.0001)
ITT (rucaparib n = 375; placebo n = 189)	10.8 vs. 5.4 (p < 0.0001)	0.365 (p < 0.0001)	13.7 vs. 5.4 (p < 0.0001)	0.354 (p < 0.0001)
Exploratory Analysis of Non-nested Subgroups				
Non-tBRCA LOH+ (rucaparib n = 106; placebo n = 52)	9.7 vs. 5.4 (p < 0.0001)	0.440 (p < 0.0001)	11.1 vs. 5.6 (p = 0.0114)	0.554 (p = 0.0135)
Non-tBRCA LOH- (rucaparib n = 107; placebo n = 54)	6.7 vs. 5.4 (p = 0.0040)	0.583 (p = 0.0049)	8.2 vs. 5.3 (p = 0.0002)	0.470 (p = 0.0003)

Abbreviations: HRD = homologous recombination deficiency; IRR = independent radiology review; ITT = intent-to-treat; LOH = loss of heterozygosity; non-tBRCA LOH+ = patients without a deleterious tBRCA mutation and with percent of tumor genome LOH ≥ 16%; non-tBRCA LOH- = patients without a deleterious tBRCA mutation and with percent of tumor genome LOH < 16%; PFS = progression-free survival; tBRCA- = tumor tissue mutation in BRCA1 or BRCA2, includes germline BRCA and somatic BRCA mutations.

^a Stratified log-rank analysis.

^b Cox proportional hazard model.

1.3.2.2.3 OVERVIEW OF SAFETY

Results of an integrated safety analysis for rucaparib treatment in over 1,000 patients with ovarian or prostate cancer who received 600 mg BID rucaparib showed that the most common treatment-emergent adverse events (TEAEs) reported were primarily mild to moderate (Grade 1-2) in severity and included gastrointestinal disorders (nausea, vomiting, diarrhea, and constipation), asthenia/fatigue, anemia/decreased hemoglobin, alanine aminotransferase (ALT)/aspartate aminotransferase (AST) increased, decreased appetite, and dysgeusia. The most common TEAEs ≥ Grade 3 included anemia/decreased hemoglobin, ALT/AST increased, neutropenia/decreased absolute neutrophil count (ANC), and asthenia/fatigue.

The laboratory abnormalities were consistent with the TEAEs, with decreased hemoglobin (and associated increase in mean corpuscular volume [MCV] and mean corpuscular hemoglobin [MCH]), increased ALT, increased AST, and increased serum creatinine, most commonly occurring. Decreased platelets, neutrophils, leukocytes, lymphocytes, and increased cholesterol were observed to a lesser extent. The transient elevations in ALT/AST with rucaparib treatment in either the treatment or maintenance settings were not associated with abnormal increases in bilirubin or other criteria for drug-induced hepatotoxicity and generally resolved over time. Furthermore, no cases met Hy's law criteria for drug-induced liver injury (DILI) and few patients discontinued rucaparib due to ALT/AST elevations.^{13,16} Similarly, elevations in creatinine were self-limiting and stabilized over time. Elevated serum creatinine levels resolved upon interruption or discontinuation of rucaparib, were not accompanied by changes in blood urea nitrogen (BUN), and did not lead to discontinuation of rucaparib treatment.^{13,16} Increased creatinine with rucaparib treatment is likely due to the potent inhibition by rucaparib of MATE1 and MATE2-K renal transporters (Section 1.3.2.1). Effects on cardiac channel activity in vitro and a comprehensive assessment of the effects of rucaparib on electrocardiogram (ECG) parameters in cancer patients demonstrated a low risk of cardiac effects by rucaparib.

Myelodysplastic syndrome (MDS) and acute myeloid leukemia (AML) are considered adverse events of special interest (AESIs), as these events have been observed in patients exposed to cytotoxic chemotherapy (eg, platinum and anthracyclines) used for treatment of ovarian cancer as well as with PARP inhibitors, including rucaparib. Patients in rucaparib clinical studies diagnosed with MDS or AML had significant confounding risk factors including prior cytotoxic chemotherapy, as well as a deleterious BRCA mutation.^{39,40} Based on these confounding factors, there is insufficient scientific evidence to conclude that MDS and AML are causally related to rucaparib. More information on AESIs for rucaparib is provided in the rucaparib IB.

1.4 Rationale for this Study of Rucaparib

Patients with MIBC represent a population with advanced disease, poor prognosis, and unmet need. The median OS in this patient population is 15 months. Response rates to initial treatment with cisplatin-based chemotherapy range from 49% to 72%; however, most patients will have disease relapse within 9 months following initial treatment.^{4,5} Furthermore, the majority of patients will progress within 2 to 3 months following failure on first- and/or second-line therapy.⁶ There are limited treatment options beyond first- or second-line treatment with platinum-containing chemotherapy and/or an immune checkpoint inhibitor, therefore additional therapies for the treatment of patients with MIBC beyond first- or second-line are needed. Treatment within clinical studies is considered an appropriate treatment option for these patients.¹⁸

Homologous recombination pathway defects may be responsible for the genetic instability observed in many cancers including ovarian cancer and urothelial cancer. For ovarian cancer, it is estimated approximately 50% of high-grade serous ovarian cancer patients have alterations in HRR genes.⁴¹ Clinical data with rucaparib have shown patients with and without a BRCA (germline or somatic) mutation benefit from rucaparib treatment in both the treatment and maintenance settings of ovarian cancer.^{16,31} While patients with a BRCA

mutation derived the most benefit, patients without evidence of a BRCA mutation also derived significant benefit suggesting an incomplete understanding of biomarkers involved in sensitivity to a PARP inhibitor.¹⁶ Similar to ovarian cancer, an analysis of TCGA bladder cancer data set (<http://cancergemone.nih.gov>) indicates that approximately 60% of bladder cancer tumors may have alterations in HRR genes and/or other genomic/epigenetic deficits that can drive HRD (Clovis, data on file). The presence of HRD in tumors has been demonstrated to predict response to cisplatin-based chemotherapy in bladder cancer.^{10,11} Based on these analyses and data, bladder cancer patients have the potential to benefit from treatment with a PARP inhibitor.

The purpose of this study is to assess the efficacy and safety of rucaparib in patients with locally advanced unresectable or metastatic urothelial bladder cancer. The study will enroll approximately 200 patients, regardless of HRD status, who have received 1 or 2 prior treatment regimens. Enrollment of patients, regardless of HRD status, who have received ≤ 2 prior treatments, is appropriate given that available treatment options are limited and both HRD-positive and HRD-negative patients may potentially respond to treatment with rucaparib. Primary efficacy will be assessed in a prospectively defined HRD-positive population as well as the intent-to-treat (ITT) population. Additional secondary and exploratory efficacy and safety endpoints will also be evaluated in HRD subgroups and the ITT population.

2 STUDY OBJECTIVES AND ENDPOINTS

Primary, secondary, and exploratory objectives and endpoints are shown in [Table 2](#).

Table 2. Primary, Secondary, and Exploratory Objectives and Endpoints

Primary Objectives	Primary Endpoints
To evaluate objective response rate (ORR) in molecularly-defined homologous recombination deficiency (HRD)-positive and intent-to-treat (ITT) populations using a prospectively defined molecular signature.	ORR per Response Evaluation Criteria in Solid Tumor (RECIST) Version 1.1 (v1.1), as assessed by investigator, in HRD-positive and ITT populations
Secondary Objectives	Secondary Endpoints
To evaluate duration of response (DOR)	DOR per RECIST v1.1, as assessed by investigator
To estimate progression-free survival (PFS)	Disease progression according to RECIST v1.1, as assessed by the investigator, or death due to any cause
To estimate overall survival (OS)	OS
To evaluate safety and tolerability of rucaparib	Incidence of adverse events (AEs), clinical laboratory abnormalities, changes in ECGs and vital signs, and dose modifications
To evaluate steady-state pharmacokinetics (PK) of rucaparib	Trough (C_{min}) level rucaparib concentrations
Exploratory Objectives	Exploratory Endpoints
To assess biomarkers that correlate with response to rucaparib	Biomarkers correlated with response to rucaparib
To evaluate circulating cell-free tumor DNA (ctDNA) as a molecular marker of response to rucaparib	Association of cancer-related mutations detected in baseline ctDNA samples with response to rucaparib
To assess molecular changes over time in plasma and tumor samples	Association of changes in cancer-related mutations detected in plasma and tissue samples over time with response to rucaparib
To evaluate biomarkers associated with resistance to rucaparib	Biomarkers associated with resistance to rucaparib

3 INVESTIGATIONAL PLAN

3.1 Overall Study Design and Plan

This is a Phase 2 multicenter, open-label study evaluating rucaparib for treatment of patients with locally advanced unresectable or metastatic urothelial carcinoma. This study will enroll patients with measurable disease per RECIST v1.1. All patients must have received 1 or 2 prior treatment regimens and have radiologic progression during or after the most recent regimen. Patients who have received prior PARP inhibitor treatment will be excluded. Tumor tissue will be analyzed to determine the percentage of genomic LOH³¹ and patients will be classified as HRD-positive or HRD-negative for efficacy analyses based on a prespecified LOH cut-off defined in the statistical analysis plan (SAP).

This study consists of a Screening Phase (Section 3.1.1), a Treatment Phase (Section 3.1.2) and a Post-treatment Phase (Section 3.1.3). Patients will receive rucaparib monotherapy in the Treatment Phase, and will undergo procedures and assessments including regular safety and efficacy evaluations during the entire conduct of the study.

3.1.1 Screening Phase

After providing consent to participate, patients will undergo procedures and assessments as described in Section 7.3 within 28 days prior to the first dose of rucaparib. During this period, unless otherwise required by local regulations, only adverse events (AEs) which are related to protocol-mandated assessments will be reported.

During the Screening Phase, each patient, with the following exceptions, will undergo a biopsy for collection of tumor tissue. Tumor tissue samples should be from primary or metastatic soft tissue tumor (see Section 7.6.5.1 for details). Patients who had tumor tissue collected as part of standard of care \leq 6 months prior to the first planned dose of rucaparib and had no intervening anti-cancer treatments during this period are not required to have a biopsy provided that adequate tumor tissue can be provided for analysis. Whenever possible, submission of additional archival tumor tissue (with no limit on date of collection) is strongly encouraged. If tissue is unable to be submitted prior to the first dose, it must be submitted to the sponsor's central laboratory by Cycle 2 Day 1. Tumor tissue will be analyzed for HRD signature status. If an actionable mutation, as defined by the American College of Medical Genetics and Genomics (<https://www.ncbi.nlm.nih.gov/clinvar/docs/acmg/>), is detected from this testing, the finding will be made available to the investigator provided the results are generated from a Clinical Laboratory Improvement Amendments (CLIA)-certified laboratory and the patient has consented to receive the results.

Additional screening assessments will include collection of the patient's medical information and demographics, prior anti-cancer treatments, prior and current medications and procedures, physical exam, vital signs, 12-lead ECG, ECOG performance status, laboratory safety assessments, urinalysis, serum pregnancy tests (for women of child-bearing potential only), and tumor assessments by computed tomography (CT) scans or magnetic resonance imaging (MRI) scans (if required by local authorities) and a baseline biomarker blood sample for circulating cell-free tumor DNA (ctDNA) analysis as described in Section 7.3.

Enrollment will require prospective sponsor (or designee) review and confirmation of eligibility, including, but not limited to:

- details of prior therapy for locally advanced unresectable or metastatic urothelial carcinoma
- screening laboratory assessments

3.1.2 Treatment Phase

Rucaparib will be administered at a starting dose of 600 mg BID. During the Treatment Phase, patients will undergo procedures and assessments including regular evaluations for safety and efficacy as described in [Section 7.4](#). A blood sample will be collected on Cycle 1 Day 1 and stored for subsequent genomic DNA testing and exploratory analysis. Blood for ctDNA analysis will be collected before dosing on Day 1 of Cycles 1, 2, 3, and at every 8 weeks thereafter coinciding with radiographic scans.

Tumor assessments by CT will be performed at the end of every 8 calendar weeks (± 7 days) from Cycle 1 Day 1 up to 18 months and every 12 calendar weeks (± 7 days) thereafter, and at the End of Treatment Visit, if applicable. RECIST v1.1 criteria will be used to document radiologic response. MRI scans may be performed in place of CT scans if required by local authorities. Any drug modifications (interruption, dose reduction, or discontinuation) should be documented in the electronic Case Report Form (eCRF) and source documents. If study treatment is interrupted, tumor assessments will not be delayed and will be performed on the regular study schedule. Copies of all radiologic scans (and other imaging, as appropriate) will be collected.

Patients will receive rucaparib until confirmed radiologic disease progression assessed by investigator based on RECIST v1.1, unequivocal clinical disease progression, unacceptable toxicity or inability to tolerate further treatment, loss to follow-up, death, or withdrawal of consent. Palliative radiation therapy on lesions not considered target lesions for RECIST v1.1 assessments is allowed and should not result in discontinuation of rucaparib therapy. Patients who discontinue study treatment for reasons other than radiologic disease progression or death, should continue radiologic tumor assessment performed as described in [Section 3.1.3](#).

If a patient has radiologic progression per RECIST v1.1, but is deriving clinical benefit in the opinion of the investigator, then continuation of treatment beyond progression is allowed per [Section 5.4.3](#). In such cases, the decision to continue treatment should be documented in the source documents and the patient must provide additional consent prior to continuing treatment with rucaparib. These patients will continue to undergo all protocol required assessments specified in [Table 5](#).

Patient safety will be monitored on a regular basis using procedures and assessments described in [Section 7](#) and [Section 11.4](#). Safety data will be periodically reviewed by the Data Monitoring Committee (DMC) as described in [Section 11.6](#). The DMC will comprise coordinating investigators and sponsor representatives. The DMC will meet after the first 20 patients received rucaparib for at least 1 cycle or discontinued study treatment and approximately every 6 months thereafter until completion of the study.

3.1.3 Post-treatment Phase

The sponsor or designee should be notified of all treatment terminations as soon as possible. The date and reason for cessation of rucaparib must be documented in the eCRF and source documents. Patients will undergo procedures and assessments during the Post-treatment Phase as described in [Section 7.5](#). Upon treatment discontinuation, patients will have an End of Treatment Visit ([Section 7.5.1](#)), a 28-day Follow-up Visit ([Section 7.5.2](#)), and then will proceed to long-term follow-up ([Section 7.5.3](#)).

All patients enrolled into the study will provide an End of Treatment Visit blood sample for ctDNA analysis. An optional tumor biopsy will be collected prior to the start of subsequent anti-cancer therapy from patients who experience radiographic or unequivocal clinical disease progression and who provide additional consent.

For patients who had their last tumor assessment ≥ 8 weeks prior to End of Treatment Visit, a tumor assessment must be performed.

If treatment was discontinued for reasons other than radiologic disease progression or death, radiologic tumor assessment (using the same methodology as was used at initial study screening [eg, CT scan]) will continue until confirmed radiographic disease progression by RECIST v1.1 criteria as assessed by the investigator, loss to follow-up, withdrawal of consent, death, initiation of subsequent treatment, or study closure. For these patients, tumor assessments should continue to be performed at the end of every 8 calendar weeks (± 7 days) relative to Cycle 1 Day 1 up to 18 months and then every 12 calendar weeks (± 7 days) thereafter, until confirmed radiologic disease progression by RECIST v1.1 criteria as assessed by the investigator, loss to follow-up, withdrawal of consent, death, or study closure.

[figure not shown]
Ongoing serious adverse events (SAEs), AESIs, and treatment-related Grade 3/4 AEs will be followed until either resolution or stabilization has been determined or until loss to follow-up. After the 28-day Follow-up Visit, related SAEs and all AESIs (irrespective of causality) need to be reported.

All patients will be followed for survival and subsequent treatments every 12 weeks (± 14 days) relative to the last dose of rucaparib until death, loss to follow-up, withdrawal of consent, or study closure.

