7.5.3 Long-term Follow-up

Patients who complete a 28-day Follow-up Visit after the last dose of rucaparib will continue in long-term follow-up as described below.

- If applicable, tumor assessment (using the same methodology as was used at initial study screening [eg, CT scan or MRI scan if required by local authorities]) when the reason for treatment discontinuation was other than death or disease progression based on radiologic assessment and it has been ≥ 8 weeks since last scan or disease progression was noted on the last scan. Tumor assessment should continue to be performed at the end of every 8 calendar weeks (± 7 days) relative to Cycle 1 Day 1 up to 18 months, then every 12 calendar weeks (± 7 days), until confirmed radiologic disease progression by RECIST v1.1 criteria as assessed by the investigator, loss to follow-up, withdrawal, death, initiation of subsequent treatment, or study closure.
- All patients discontinued from treatment, regardless of reason, will be followed and information collected for subsequent treatments and survival every 12 weeks from last dose of rucaparib until death, loss to follow-up, withdrawal of consent from study, or closure of the study. Follow-up can be performed via the telephone and can be completed to coincide with scheduled tumor assessments.
- SAEs related to rucaparib and all AESIs, irrespective of causality, are to be reported as specified in [Section 8.9](#).

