7.6.3 Efficacy Evaluations

Target and non-target lesions will be evaluated for evidence of radiographic response based on RECIST v1.1 criteria.

Tumor assessments will be performed during screening (baseline), at the end of every 8 calendar weeks (± 7 days) relative to the first dose of rucaparib (Cycle 1 Day 1) up to 18 months, then every 12 calendar weeks (± 7 days), until confirmed radiologic disease progression by RECIST v1.1 criteria as assessed by the investigator, loss to follow-up, withdrawal from study, death, or study closure. Tumor assessments should be performed at the time of treatment discontinuation if the reason was other than radiologically confirmed disease progression and it has been ≥ 8 weeks since the last assessment. If treatment was discontinued for reasons other than radiologic disease progression or death, radiologic tumor assessment (using the same methodology as was used at initial study screening) will continue until confirmed radiographic disease progression by RECIST v1.1 per investigator, death, loss to follow-up, withdrawal from the study, study closure, or initiation of subsequent treatment.

Tumor assessments should consist of clinical examination and appropriate imaging techniques (ie, CT scans of the chest, abdomen, and pelvis with appropriate slice thickness per RECIST v1.1); other studies (magnetic resonance imaging (MRI), X-ray, positron emission tomography [PET]/CT, and ultrasound) may also be performed if required. MRI may be used in place of CT scans for assessment of target lesions if required by local authorities. If a site can document that the CT performed as part of a PET/CT is of identical diagnostic quality to a diagnostic CT (with IV and oral contrast) then the CT portion of the PET/CT can be used for RECIST measurements. All sites of disease should be followed and the same methods used to detect lesions at baseline are to be used to follow the same lesions throughout the clinical study. If a patient has known brain metastases, this disease should be evaluated at each required assessment time.

If a complete response (CR) or partial response (PR) is noted, confirmatory scans should be performed at least 4 weeks after response was first documented.

Copies of CT scans (and other imaging, as appropriate) will be collected from all patients. IRR may be conducted on all or a subset of CT scans.

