9.2 Secondary Efficacy Analyses

9.2.1 Duration of Confirmed Response

The duration of confirmed response is defined as the time from the date that a response is first documented per RECIST v1.1 by the investigator to the time that progression is first documented per RECIST v1.1 by the investigator, plus 1 day.

The duration of confirmed response will be analyzed and summarized in a Kaplan-Meier plot. Any patient with an ongoing response at the time of data cut-off for analysis will be censored at the date of the last post-baseline scan. In the case of a low censoring rate, the duration of response may be summarized with descriptive statistics.

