9.2.2 Progression-free Survival

Progression-free survival (PFS) is defined as the time from first dose of rucaparib to the date of first objective evidence of progression documented by the investigator per RECIST v1.1 or death due to any cause, whichever occurs first, plus 1 day. Patients without a documented event of progression will be censored on the date of their last adequate post-baseline tumor scan or date of first dose of study drug if no tumor scans have been performed. If a patient discontinues study drug due to something other than PD and subsequently begins another anti-cancer therapy (ACT) prior to a PFS, that patient will be censored at the last tumor scan prior to the start of ACT. However, PFS events occurring more than 90 days after discontinuation of study drug, but prior to start of subsequent ACT, will not be included in

the analysis and such patients will be censored at their last scan prior to the end of the 90-day window.

PFS will be summarized in a Kaplan-Meier plot; however in the case of a low censoring rate, it may be summarized with descriptive statistics.

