Progressive Disease	At least a 20% increase in the sum of the LD of target lesions, taking as reference the smallest sum on study (this includes the baseline sum if that is the smallest on study). In addition to the relative increase of 20%, the sum must also demonstrate an absolute increase of at least 5 mm. The appearance of one or more new lesions is also considered progression.

Abbreviations: LD = longest diameter; PD = progressive disease.

Evaluation of Nontarget Lesions	
Complete Response	Disappearance of all nontarget lesions and normalization of tumor marker level.
Stable Disease/Incomplete Response	Persistence of 1 or more nontarget lesion(s) or/and maintenance of tumor marker level above the normal limits.
Progressive Disease	Appearance of 1 or more new lesions and/or unequivocal progression of existing nontarget lesions.

If tumor markers are initially above the institutional ULN, they must normalize for a patient to be considered a complete responder.

Evaluation of Best Overall Response

The best overall response is the best response recorded from the start of the treatment until disease progression/recurrence (taking as reference for PD the smallest measurements recorded since the treatment started). The patient's best response assignment will depend on the achievement of both measurement and confirmation criteria.

Evaluation of Best Overall Response			
Target Lesions	Nontarget Lesions	New Lesions	Overall Response
CR	CR	No	CR
CR	Non-CR/non-PD	No	PR
CR	Not evaluated	No	PR

Evaluation of Best Overall Response				
Target Lesions		Nontarget Lesions	New Lesions	Overall Response
PR		Non-PD or not evaluated	No	PR
SD		Non-PD or not evaluated	No	SD
Not Evaluated		Non-PD	No	NE
PD		Any	Yes or No	PD
Any		PD	Yes or No	PD
Any		Any	Yes	PD
CR	=	complete response		
NE	=	not evaluable.		
PD	=	progressive disease		
PR	=	partial response		
SD	=	stable disease		

Patients with a global deterioration of health status requiring discontinuation of treatment without objective evidence of disease progression at that time should be classified as having symptomatic deterioration. Every effort should be made to document the objective progression, even after discontinuation of treatment.

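### The protocol contradicts itself on whether scans stop when a new anti-cancer therapy starts, and neither ORR nor DOR is cut at that point, so a scan taken after a switch could be credited to rucaparib

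*Protocol*

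**What the plan says.** **When scans stop.** Protocol 3.1.3 gives two lists for the same patients, those who stop rucaparib for a reason other than radiologic progression or death. The first ends scanning at "loss to follow-up, withdrawal of consent, death, initiation of subsequent treatment, or study closure". The next sentence, which sets the scan interval, continues "until confirmed radiologic disease progression by RECIST v1.1 criteria as assessed by the investigator, loss to follow-up, withdrawal of consent, death, or study closure" and leaves out the start of subsequent treatment.

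Protocol 7.6.3 has the same split. Its general sentence ends with "loss to follow-up, withdrawal from study, death, or study closure". Its later sentence, on patients who are off treatment without progression, ends with "death, loss to follow-up, withdrawal from the study, study closure, or initiation of subsequent treatment".

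Elsewhere the stop at subsequent treatment is present: in the synopsis (Post-treatment Phase and Efficacy Assessments), in Table 5 footnote r, and in 7.5.3 ("loss to follow-up, withdrawal, death, initiation of subsequent treatment, or study closure"). Counting the including sentences of 3.1.3 and 7.6.3, six statements include it and two omit it. The scan at the 28-day Follow-up Visit (7.5.2) applies to every patient without radiographic progression and makes no exception for new therapy.

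**What the analysis uses.** SAP 9.1 defines ORR as confirmed CR or PR and does not mention subsequent therapy. SAP Appendix 1 sets the window: "The best overall response is the best response recorded from the start of the treatment until disease progression/recurrence". For DOR, SAP 9.2.1 says an ongoing response "will be censored at the date of the last post-baseline scan". For PFS only, SAP 9.2.2 deals with a patient who stops for a reason other than PD and then starts another therapy: "that patient will be censored at the last tumor scan prior to the start of ACT". Protocol 9.5.2.2 has no such rule for PFS.

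**The concern.** The SAP foresees the patient who leaves rucaparib without RECIST progression and moves to another drug. It protects a secondary endpoint from that patient's later scans, but not the primary endpoint or DOR. The route is a planned one: Protocol 10.1 requires discontinuation for unequivocal clinical progression that calls for an immediate change of systemic therapy, and toxicity is another route. In neither case need RECIST progression be on record, so the best-response window stays open.

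Three things can go wrong if such a patient is scanned after the switch:

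- Tumour shrinkage on the next drug can be recorded as a rucaparib response.
- A response first seen on rucaparib can be confirmed by a scan taken on the next drug.
- A rucaparib responder who switches can have DOR extended by the next drug.

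In a single-arm trial judged against a fixed rate of 10%, no control group absorbs such an error.

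**Working it through.** **1. Would the stated rules admit a post-switch scan?**

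| Endpoint | What closes the window | Closed by new therapy? |
|---|---|---|
| ORR (SAP 9.1, Appendix 1) | progression or recurrence | no |
| DOR (SAP 9.2.1) | progression, or the last post-baseline scan | no |
| PFS (SAP 9.2.2) | event, or the last scan before new therapy | yes |
| PFS (Protocol 9.5.2.2) | event, or the last adequate assessment | no |

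SAP 10.1 adds that all data are to be used as far as possible, so it does not exclude these scans.

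**2. Reproduce the plan's own figures.** Inputs from SAP Appendix 2 (Protocol Appendix 4): N = 200, null rate 0.10, prior Beta(0.1, 0.9), success if Pr(p > 0.10 | data) > 0.95.

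- Posterior at 28/200: Pr(Beta(28.1, 172.9) > 0.10) = 0.9585. At 27/200: 0.9355. The boundary is 28/200 (14.0%).
- P(X ≥ 28 | 200, 0.10) = 0.0434 and P(X ≥ 28 | 200, 0.20) = 0.9890. The appendix gives 0.043 and 0.989 for the fixed design.
- With the futility minima of 5/60 and 13/120, exact recursion gives 0.0415 and 0.9849. The simulated values in the row labelled Unadjusted are 0.039 and 0.985.

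The plan's figures are therefore right, provided every counted response is a rucaparib response.

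**3. Effect of a fixed number k of misattributed responses.** If k responses come from the next drug, rucaparib needs only 28 − k. At a true ORR of 10%, fixed N:

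| k | needed from rucaparib | P(X ≥ 28 − k) |
|---|---|---|
| 0 | 28 | 0.043 |
| 1 | 27 | 0.067 |
| 2 | 26 | 0.100 |
| 3 | 25 | 0.145 |
| 4 | 24 | 0.202 |

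This step assumes nothing about how often patients switch; it shows what each error costs. In the reported ORR, each one adds 1/200 = 0.5 points.

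**4. Illustration with an assumed switch fraction.** Let f be the share of rucaparib non-responders who stop without RECIST progression, start a new drug and are still scanned. The documents do not give f; 0.5% to 10% is assumed. Let q be the ORR of the next drug: Protocol 1.1.2 gives 10% to 20% for single-agent chemotherapy and 15% to 21% for checkpoint inhibitors, so q runs from 10% to 21%. Only non-responders can be converted, so

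observed rate = 0.10 + 0.90 × f × q.

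| f | q | extra responders = 180 × f × q | observed rate | P(X ≥ 28) |
|---|---|---|---|---|
| 0.5% | 10% | 0.09 | 0.1005 | 0.046 |
| 1% | 21% | 0.38 | 0.1019 | 0.053 |
| 5% | 10% | 0.90 | 0.1045 | 0.068 |
| 5% | 21% | 1.89 | 0.1095 | 0.105 |
| 10% | 21% | 3.78 | 0.1189 | 0.205 |

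The range is about 4.6% to 20.5%. With the futility looks the top figure is 19.8%.

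**The case against.** The strongest reply is that the protocol mostly prevents the problem at source. Six statements stop scans at subsequent treatment, among them the schedule table and the long-term follow-up section that sites work from. The omitting sentence in 3.1.3 sets a scan interval for patients whose stop rule has just been given, and the omitting sentence in 7.6.3 is a general one. Both look like editorial slips. If scanning does stop, the last post-baseline scan is in effect the last scan before new therapy, and a next-drug response cannot collect both an initial scan and a confirmation at least 4 weeks later.

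Much of this stands. A reader might infer that the plan directs sites to keep scanning after a switch; the documents do not support that, because they say both things and more often say stop. The 28-day visit scan does remain open to a patient already on a new drug. That single scan could confirm an earlier response or extend DOR, though alone it cannot create a confirmed response.

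The reply is also right about size. The fraction f has no source in the documents. The quoted next-drug ORRs are measured from each drug's own baseline, whereas here PR needs a 30% fall from the rucaparib baseline without earlier progression. Some patients will already have had a checkpoint inhibitor. A reader might infer a type I error of about 20%; that is only the top of an assumed range, and at f of 0.5% to 1% the rate is about 4.6% to 5.3%.

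Finally, PFS is protected in the SAP only, so it would be wrong to say that the two documents together consistently protect it.

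**Conclusion.** The point holds as a contradiction between scan stop lists combined with a missing analysis rule for ORR and DOR. Followed literally, the stated best-response window and DOR censoring would use a post-switch scan wherever one exists. The documents do not say how many patients this would reach, and the number is probably small. It merits correction because the success boundary has little slack: at a true ORR of 10%, a single misattributed response takes the fixed-sample false-positive rate from 4.3% to 6.7%, above the stated 5% level, and a second takes it to 10.0%. Those figures rest on the plan's own success rule and on the given count of misattributed responses. The 4.6% to 20.5% range also rests on the assumed f and on q taken from Protocol 1.1.2, and is an illustration only. The plan's stated power and type I error are not in error.

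**What to change.** - **SAP 9.1 and Appendix 1:** count only responses first documented and confirmed on scans before the first subsequent anti-cancer therapy. Keep all other patients in the denominator as non-responders.
- **SAP 9.2.1:** censor DOR at the last scan before that therapy, matching SAP 9.2.2.
- **Protocol 3.1.3 and 7.6.3:** reconcile the scan stop lists with each other and with the remaining statements.

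The cost is a sentence or so in each SAP section and an editorial correction to the protocol. Subsequent treatments are already collected in follow-up (Protocol 3.1.3 and 7.5.3), so no new data are needed. The downside is that a response confirmed only after a switch would no longer count, so ORR may be slightly lower.
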